3.2 Populations

The Efficacy Population will include all patients who meet all eligibility, are treated with Varithena®, and who have at least one post-treatment primary endpoint assessment. This will be the primary population and all analyses will be performed on the efficacy population.

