## 6.2.2 Exclusion Criteria

---

Subjects must not meet any of the following exclusion criteria:

- 8 Contraindications to Varithena® in accordance with the FPI
- 9 Any serious concomitant disease, per physician's discretion, that confounds wound healing, including malignant changes of wound
- 10 Concomitant heat ablation, or heat ablation of index leg within 6 weeks prior to treatment with Varithena®
- 11 Significant arterial disease or ABPI ≤ 0.8
- 12 In the opinion of Investigator, wound would close within 12 weeks without additional treatment

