#### 10.2.1 Analysis Populations

---

The Efficacy Population will include all patients who are treated with Varithena® and who have at least one post treatment primary endpoint assessment.

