1.3 Study endpoints

The primary endpoints of the study are:

- Rate of epithelial migration (mm/week) measured by wound perimeter on photograph
- Wound closure at 12 weeks (± 1 wk) post-treatment
- Time from initial treatment with Varithena® to wound closure

The secondary endpoints of the study are:

- Percent of wounds remaining closed at 3 months (± 1 wk) post-wound closure date, non-healed wounds are not included in percent calculation
- For healed wounds, rate of VLU recurrence (at same site)
- Change in pain on NPRS compared to baseline at 12 weeks (± 1 wk), 6 months (± 1 wk), 12 months (± 1 wk) post-treatment
- Change on Euroqol five dimension five level questionnaire (EQ-5D-5L) quality of life assessment compared to baseline at 12 weeks (± 1 wk) and 12 months (± 1 wk) post-treatment
- Change in Venous Clinical Severity Score (VCSS) from baseline to 12 week (± 1 wk) and 12 month (± 1 wk) follow-up
- Number of ulcer-free weeks defined as weeks from time of closure (complete epithelialization is recorded) to date of recurrence (at same site) or last contact if no recurrence (at study completion or withdrawal)

2 Changes to protocol analysis

The interim analyses were expanded to look at hospitalization and safety information. Please see section 3.8 for further details.

Additional exploratory analyses from the Wound Health Index (WHI) will not be conducted.

NPRS analyses will use data from both the sDCT and the electronic data capture (EDC). The analysis will be summarized by each week through 12 weeks, 6 months and 12 months post-treatment. Additionally, the categories by severity will not be summarized but rather the numerical scale will be summarized and presented in a shift table. Refer to section 3.5.2 for further details.

Sub-group analyses will not be performed. There is not enough data collected for the analyses to be meaningful.

3 Statistical methods and analysis

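### SAP 3.2 narrows the protocol's Efficacy Population to patients who meet every eligibility criterion, does not declare the change, and plans no all-treated analysis

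*SAP*

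**What the plan says.** Protocol section 10.2.1 sets two conditions: "The Efficacy Population will include all patients who are treated with Varithena® and who have at least one post treatment primary endpoint assessment".

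SAP section 3.2 sets three. Its population is "all patients who meet all eligibility, are treated with Varithena" and have a primary endpoint assessed afterwards. It then makes this the only analysis set: "This will be the primary population and all analyses will be performed on the efficacy population".

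SAP section 2 is where departures from the protocol's analysis are recorded. It lists four: a wider interim analysis ("The interim analyses were expanded to look at hospitalization and safety information"), no Wound Health Index analyses, a different handling of NPRS, and no sub-group analyses. The analysis population is not among them.

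The eligibility criteria are in protocol sections 6.2.1 and 6.2.2. Exclusion 12 reads "In the opinion of Investigator, wound would close within 12 weeks without additional treatment". Exclusion 9 leaves to the physician whether a concomitant disease is serious and confounds healing. Exclusion 11 combines a numeric ABPI limit with an undefined category of significant arterial disease.

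Under protocol sections 8.2.2 and 8.2.3, eligibility is reviewed before a subject is entered and given a code. SAP section 3.3.3 says that eligibility deviations are kept in a spreadsheet outside the EDC.

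**The concern.** The added condition can only act in one way: it takes out patients who were treated and assessed, whom the protocol would count. In an open-label, single-arm registry whose purpose is estimation, the denominator is a large part of the result. No control arm is affected in the same way, and outcomes are visible to those handling the data.

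Exclusion 12 concerns closure by 12 weeks, the same event as one of the primary endpoints. Exclusion 9 turns on whether a disease confounds healing. If criteria of this kind were looked at again once healing was known, the answer could lean on the outcome. The plan does not provide for such a second look, but it does not close it off either.

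The scope also matters. Read literally, the restriction reaches the listing of treatment-related serious adverse events (SAP 3.7) and the interim review of hospitalizations and related serious adverse events that can stop the study (SAP 3.8). A treated patient later found ineligible could be missing from both.

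**Working it through.** The plan gives no figure to reproduce: there is no sample size calculation, no hypothesis test, and no expected number of ineligible patients. The check is a comparison of texts, followed by an illustration of scale.

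**1. The two definitions**

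| Condition | Protocol 10.2.1 | SAP 3.2 |
|---|---|---|
| Treated | yes | yes |
| Primary endpoint assessed after treatment | yes | yes |
| All eligibility criteria met | no | yes |

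The third row is a restriction, not added detail. Protocol 10.1 lets the SAP describe methods more fully, but a narrower primary population is a change and belongs in SAP section 2.

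**2. Who would be removed.** Only patients who passed the entry check, were treated and assessed, and were found ineligible later. SAP 3.3.3 plans to count eligibility deviations, so the sponsor allows that such patients may exist.

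**3. Which criteria could be disputed.** There are 12 criteria. Age, ulcer duration, reflux time, ABPI and the heat-ablation interval can be checked against pre-treatment records. Exclusions 9 and 12, and the arterial-disease wording of exclusion 11, rest on judgement.

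**4. Who decides, and when.** Neither document names the person who rules a treated patient ineligible. Neither sets a date for the ruling, or requires it before database lock and without sight of outcomes.

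**5. What the reports would show.** SAP 3.3.1 gives the number screened and the number in the Efficacy Population. SAP 3.3.3 gives the number with deviations. Neither is required to show how many treated patients were removed for ineligibility, or on which criterion.

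**6. Scale, under assumptions.** Let *f* be the fraction of treated, assessed patients removed, *p* the 12-week closure rate in those kept, and *q* the rate in those removed.

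- Rate in all treated, assessed patients = (1 - *f*)*p* + *fq*
- Reported rate minus that rate = *f*(*p* - *q*)

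With *p* = 60% assumed:

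| *f* | *q* | All treated, assessed | Reported | Difference (points) |
|---|---|---|---|---|
| 5% | 30% | 0.95×60 + 0.05×30 = 58.5% | 60% | +1.5 |
| 10% | 30% | 0.90×60 + 0.10×30 = 57.0% | 60% | +3.0 |
| 5% | 80% | 0.95×60 + 0.05×80 = 61.0% | 60% | -1.0 |
| 10% | 80% | 0.90×60 + 0.10×80 = 62.0% | 60% | -2.0 |

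**7. Outer bound.** Suppose all those removed share one outcome. Take 200 treated, assessed patients with 120 closures: 60.0%, Clopper-Pearson 95% CI 52.9-66.8.

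| Removed | All non-closers | All closers |
|---|---|---|
| 10 | 120/190 = 63.2% (55.9-70.0) | 110/190 = 57.9% (50.5-65.0) |
| 20 | 120/180 = 66.7% (59.3-73.5) | 100/180 = 55.6% (48.0-62.9) |

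The shift is then 2.1 to 3.2 points at 5% removed and 4.4 to 6.7 points at 10%. Here 60% is the rate before removal; in step 6 it is the rate in those kept.

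**The case against.** The strongest reply is that the added words are nearly redundant. Protocol 8.2.2 and 8.2.3 admit only subjects found to meet every criterion, so the protocol's treated patients are already a screened group, and the SAP may merely restate this. That would explain the silence in section 2. It stands as an argument that removals will be few. It does not make the two definitions equal: the clause has an effect precisely when a patient was enrolled in error, and the protocol would count that patient.

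Second, eligibility is judged before entry, and the opinions in exclusions 9 and 12 belong to the physician or investigator at that point. Enrolling the patient records the opinion, and a wound that later closes does not show that exclusion 12 was met. Opinion-based criteria may therefore be the hardest to turn into a later failure. This is fair. What remains is that the plan does not say that the entry judgement is final.

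Third, leaving out patients who on objective pre-treatment facts fall outside the target condition is defensible, and a shift of 1-3 points is small beside an interval of about ±7 points at 200 patients. No hypothesis test depends on it. These points limit the severity. They do not justify an undeclared change with no comparison set.

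Fourth, the rule that all analyses use this set may not be meant to the letter, since SAP 3.3.1 already summarises disposition for all patients. That is possible, but nothing similar is said for the safety listing or the interim review.

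**Conclusion.** The mismatch is real and undeclared. The SAP's primary population is narrower than the protocol's, it is the only one used, and the rules for applying the added condition are not given. It should be corrected, but its likely effect is modest.

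The documents give no number of ineligible treated patients and no closure rates, so the 1-3 point range rests wholly on assumed inputs. The larger shifts in step 7 need every removed patient to have the same outcome.

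A reader might infer more than this, and the documents do not support it:

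- **That patients were, or will be, removed after outcomes are known.** No section provides for re-judging eligibility. The gap is that nothing rules it out.
- **That eligibility as a whole is a matter of opinion.** Most criteria are objective; the exceptions are exclusions 9 and 12 and part of 11.
- **That the change favours the product.** Removing non-closers raises the closure rate, while applying exclusion 12 to wounds that closed would lower it. The direction is not fixed.
- **That the restriction was written with healing results in view.** SAP section 2 says of the sub-group analyses "There is not enough data collected for the analyses to be meaningful", and the SAP cites a 2019 valuation study. These suggest that data had begun to accrue. They speak to the amount of data and the date, not to knowledge of outcomes by eligibility status.

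**What to change.** - Delete the eligibility condition from SAP 3.2, so that the primary population is the one in protocol 10.2.1.
- State that the related serious adverse event listing (SAP 3.7) and the interim safety review (SAP 3.8) cover all treated patients, whether or not they have a post-treatment assessment. Restoring the protocol definition alone would not achieve this, because that definition also requires an assessment.
- Report the eligible-only subset as a sensitivity analysis of the primary endpoints, with the number removed and the criterion each patient failed.

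If the sponsor prefers to keep the restriction, it should declare and justify it in SAP section 2 and confine it to objective pre-treatment facts. The exclusions should be decided by a named role before database lock and without outcome data, with an analysis on the protocol's population alongside.

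The cost is one sentence on the population, one on the safety denominators, and one sensitivity table. The downside is that the primary set may include a few patients enrolled in error, which the sensitivity analysis would show.

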## 10.7 Safety Analyses

---

No safety analyses are planned.

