3.7 Safety analyses

The number of serious adverse events related to Varithena[®] will be listed.

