3.8 Interim analysis

An interim futility analysis will be performed when approximately 50 – 75 patients have enrolled and completed their 12 week post-treatment follow-up. The futility analysis will look for the following safety concerns:

- Hospitalizations due to target wound
- Serious adverse events related to Varithena[®]

If the analyses show there is a high safety concern, the study will be stopped.

Additionally, the descriptive summaries for the primary endpoints (see section 3.5.1 for further details on the primary endpoints) and the secondary endpoint of EQ-5D-5L (see section 0) and NPRS (see section 0) will be performed. Information on baseline wound characteristics (see section 3.3.2), treatment history (see section 3.4.1), post-treatment ultrasound and occlusion (see section 3.4.1) will be also be summarized.

4 Appendix

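### SAP 3.2 puts all analyses on the efficacy population, so, applied literally, the related-SAE listing and the interim safety stop omit any treated subject outside that set

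*SAP*

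**What the plan says.** SAP 3.2 has a single population. Members are "all patients who meet all eligibility, are treated with Varithena" and must also have one or more post-treatment assessments of a primary endpoint. The section closes with a general rule: "This will be the primary population and all analyses will be performed on the efficacy population".

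Protocol 10.2.1 defines the same population without the eligibility condition: "The Efficacy Population will include all patients who are treated with Varithena® and who have at least one post treatment primary endpoint assessment". Protocol 10.7 states "No safety analyses are planned", so the protocol had no use for a safety set.

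The SAP then adds safety outputs. Section 2 says "The interim analyses were expanded to look at hospitalization and safety information". Section 3.7, headed as safety analyses, lists "The number of serious adverse events related to Varithena". Section 3.8 reviews hospitalisations due to the target wound and related SAEs once about 50 to 75 "patients have enrolled and completed their 12 week post-treatment follow-up", and states: "If the analyses show there is a high safety concern, the study will be stopped". Neither 3.7 nor 3.8 says which subjects are covered. Section 2 does not mention the added eligibility condition.

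**The concern.** A safety output normally covers everyone exposed to the product. Here the only defined set depends on eligibility and on having an effectiveness assessment, and neither condition has to do with exposure.

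Both conditions can remove subjects who matter for safety. Exclusion criteria 8 and 11 (protocol 6.2.2) cover contraindications in the prescribing information and significant arterial disease. The prescribing information in Appendix C lists acute thromboembolic disease as a contraindication (section 4) and warns of possible raised ischaemia risk with underlying arterial disease (section 5.2). A subject treated despite such a criterion is one whose serious event a safety review would want to see. An early death or withdrawal can also be the reason why no post-treatment assessment exists.

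The interim stop is a qualitative judgement made at about 50 to 75 subjects, so a single related SAE could weigh heavily in it.

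**Working it through.** The documents give no figure on this point that could be reproduced. The check is to place each type of subject against the definitions.

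**1. Who is in which set**

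| Subject | Protocol 10.2.1 | SAP 3.2 | All treated |
|---|---|---|---|
| (a) Treated, eligible, assessed after treatment | in | in | in |
| (b) Treated, later found ineligible, assessed | in | out | in |
| (c) Treated, eligible, no post-treatment assessment | out | out | in |
| (d) Consented, never treated | out | out | out |

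The gap is rows (b) and (c). Row (b) is created entirely by the condition that the SAP added.

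**2. Can row (b) occur?** Protocol 8.2.2 checks eligibility before a subject is entered, and 8.2.3 gives a subject code only to those who pass. Ineligibility found later is still foreseen: SAP 3.3.3 tracks and summarises eligibility deviations.

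**3. Can row (c) occur?** Protocol 9.2 counts adverse events from the start of treatment. The first scheduled follow-up photograph is at the Week 1 visit, which under protocol 8.1.3 may fall later than the first week. There is thus a period of exposure before any assessment. How many fall in row (c) depends on a term that the SAP leaves undefined. Time to closure is a primary endpoint, and SAP 3.5.1.3 censors unclosed wounds at the last date on study. If a censored time counts as an assessment, row (c) becomes narrower and may nearly vanish. Row (b) is unaffected.

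**4. Does the SAP apply its general sentence everywhere?** No. Section 3.3.1 summarises disposition for all patients. Section 3.3.3 summarises eligibility deviations, which a set limited to eligible patients would largely exclude. But 3.3.1 states its exception, and 3.7 and 3.8 state none. A programmer following the text would filter the SAE listing on the efficacy flag.

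**5. Which safety items are affected?** For related SAEs, rows (b) and (c). For target-wound hospitalisation, mainly row (b), because a subject with no post-treatment contact would usually supply no such data under any set.

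**6. Scale.** Neither document gives the number in rows (b) and (c). For the event itself, protocol 4.3 reports no serious event, fatal or not, attributed to treatment among 1333 patients. The exact two-sided 95% upper limit for 0/1333 is 1 − 0.025^(1/1333) = 0.28%. At that limit, 75 treated subjects would give 75 × 0.0028 = 0.2 related SAEs in all, before asking whether any falls outside the efficacy set. The limit may be too low for this registry: the two pivotal trials excluded, among others, patients with a history of deep vein thrombosis or pulmonary embolism and those with reduced mobility, and only 5.2% of VANISH-2 patients were in class C5 or C6.

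**The case against.** The strongest reply is that the safety route does not depend on an analysis set. Adverse events reach the sponsor on individual forms (protocol 9.2, Appendix H). Early deaths appear in the disposition table, which covers all patients and has a death category. Protocol 12.8 lets the sponsor terminate at any time, with the incidence or severity of adverse events as an example. SAP 3.7 is a listing without a denominator. The table and listing shells are a separate document that is not available here and may name the set. The sponsor may well intend all treated subjects. Reporting under protocol 9.2 also depends on whether the investigator wishes to report, which may limit the safety data more than any population definition does.

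Much of this stands, and it limits the consequence. It does not remove the point. A form on file or a death in the disposition table does not complete a listing or an interim review that was filtered on the efficacy flag, and a general right to terminate is discretionary.

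Two stronger readings are tempting. A reader might infer that treated subjects with serious events will in fact be dropped, or that a safety signal will be missed. The documents do not show this: no such subject is identified, the number may be zero, and the SAP does not follow its own sentence everywhere. A reader might also infer that 3.8 restricts the safety review to subjects who completed 12 weeks. That wording most naturally sets when the analysis takes place, not whom it covers.

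**Conclusion.** The point holds as a matter of text. SAP 3.2 states a rule, 3.7 and the safety part of 3.8 make no exception, and following the rule leaves out treated subjects later found ineligible and possibly those lost before any assessment. The first group rests only on the added eligibility condition. The second also depends on what counts as a primary endpoint assessment.

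The practical size is unknown, probably small and possibly zero. The documents support no exclusion rate, so none is assumed here. The earlier record of no attributed SAEs suggests that such events are rare, with the caveat about who entered those trials. The case for acting is that a stop decision rests on few subjects, so a single case counts, and that wording alone repairs it. If the interim analysis has already taken place, the listing in 3.7 still needs its set stated.

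**What to change.** - **SAP 3.2:** limit the general sentence to effectiveness analyses. Define a safety population of all subjects who received any Varithena, regardless of eligibility or later assessments.
- **SAP 3.7 and 3.8:** name that population for the related-SAE listing and for both interim safety items. State that the interim review covers every subject treated by the data cut-off, and that the 50 to 75 subjects completing 12 weeks set the timing only.
- **Housekeeping, SAP section 2:** list the eligibility condition as a change from protocol 10.2.1, or remove it from 3.2.

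The cost is SAP wording only: no new data, visits or protocol amendment. The downside is that safety and efficacy outputs will have different denominators, which the report must explain. The change does not make adverse event reporting more complete. It only ensures that what is reported for treated subjects is not filtered out.

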3.3 Disposition, Demographics, Baseline

3.3.1 Disposition

Patient disposition will be summarized for all patients. The following categories will be summarized:

- Number of patients screened
- Number and percentage of patients in the efficacy population
- Number and percentage of bilateral patients (2 target wounds)
- Number and percentage of patients who discontinued
- Reasons for discontinuation
 - Withdrawn
 - Lost to follow-up
 - Death
 - Study discontinued by sponsor
 - Other
- Duration on study (months)
 - Duration (months) = (earlier date of study exit/death – date of first treatment + 1)/30.4375

Reasons for discontinuation and study exit dates are collected outside of the EDC. The reasons will be mapped into the categories above by clinical and provided to statistical programming for inclusion in summary table.

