### 5.2 Design

---

[figure not shown]
This 12 month, multicenter, open-label registry is designed to collect treatment and outcome data related to subjects treated with Varithena® for GSV system and/or AASV incompetence resulting in VLU. Subjects are treated per Investigator's SoC and in accordance with the FPI and IFU. For subjects with healed ulcers during the 12 month follow-up period, VLU recurrence information is collected. Wound recurrence is defined as the reopening of a wound that was previously closed; recurrence must occur at same location.

Note: In cases of cluster wounds, Investigator collects data for a single, primary wound. If more than one wound meets eligibility criteria, Investigator determines which wound to evaluate as the primary. All endpoint measurements are collected for the primary wound.

For each subject, participation in the registry lasts approximately 12 months. Subjects are seen at the investigational site for initial treatment, about one week after treatment for initial follow-up visit (and retreatment if necessary), 12 weeks ( $\pm 1$ wk) and 12 months ( $\pm 1$ wk) after initial treatment. Between follow-up visits, and until wound closure, subjects are asked to collect weekly photographs of the wound via the sDCT during dressing changes at the wound care center (WCC).

Additionally, follow-up phone calls are placed at 3 months ( $\pm 1$ wk) post-closure and 6 months ( $\pm 1$  week) post-treatment. At that time, subjects are asked to take a picture of the wound area and complete the NPRS using the sDCT. (Figure 1)

Figure 1. Study Schematic

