1.1 Study design

This 12 month, multicenter, open-label registry is designed to collect treatment and outcome data related to patients treated with Varithena® for great saphenous vein (GSV) system and/or anterior accessory saphenous vein (AASV) incompetence resulting in venous leg ulcer (VLU). Patients are treated per Investigator's standard of care (SoC) and in accordance with the full prescribing information (FPI) and instructions for use (IFU). For patients with healed ulcers during the 12 month follow-up period, VLU recurrence information is collected. Wound recurrence is defined as the reopening of a wound that was previously closed; all references throughout protocol to wound recurrence refers to wounds that are at the same location.

Note: In cases of cluster wounds, Investigator collects data for a single, primary wound. If more than one wound meets eligibility criteria, Investigator determines which wound to evaluate as the primary/target wound. All endpoint measurements are collected for the primary wound.

For each patient, participation in the registry lasts approximately 12 months. Patients are seen at the investigational site for initial treatment, about one week after treatment for initial follow-up visit (and retreatment if necessary), 12 weeks (± 1 wk) and 12 months (± 1 wk) after initial treatment. Between follow-up visits, and until wound closure, patients are asked to collect weekly photographs of the wound via the subject data capture tool (sDCT) during dressing changes at the wound care center (WCC).

Additionally, follow-up phone calls are placed at 3 months (± 1 wk) post-closure and 6 months (± 1 week) post-treatment. At that time, patients are asked to take a picture of the wound area and complete the numeric pain rating scale (NPRS) using the sDCT.

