3.3.2 Demographic and baseline characteristics

Demographic and baseline characteristics are collected at screening. Descriptive summaries will be provided. The number and percentages (categorical variables) and descriptive statistics (continuous variables) will be summarized for the following:

Demographic

- Age (years), age group (≥ 18 to < 65 years, ≥ 65 to < 75 years, ≥ 75 years)
- Gender (Male, Female)
- Height (m)
- Weight (kg)
- BMI (kg/m^2)
- BMI Category (18.5 to < 25 , 25 to < 30 , ≥ 30)

Refer to section 0 for derivations.

Disease characteristics

- Leg of target wound (Right, left, both)
- Primary ambulatory method (Walks unaided, cane, crutches, walker, roll about, scooter, wheelchair bound, bed bound)
- Take pain medication regularly? (Yes, No)

Additionally, the following information will be summarized for each target wound:

- Received grafting for target wound? (Yes, No)
- Hospitalization for target wound? (Yes, No)
- Duration of compression therapy at baseline on current target wound (weeks)
- Compliance with compression at baseline? (Yes, No)
- Previous procedures/treatments for target wound? (Yes, No)
- If yes to previous procedure/treatment, outcome of previous treatments (Healed, Not healed)
- Whether target wound is circumferential (Yes, No)
- Wound age at first encounter (weeks)
- Total wounds or ulcers
- Number of previous ulcers
- Signs of infection or bioburden indicated by exudate (Yes, No)

Venous characteristics

The following will be summarized for each target wound:

- Duplex reflux (milliseconds)
- GSV incompetence? (Yes, No)
- AASV incompetence? (Yes, No)
- Major perforator incompetence? (Yes, No)
- Small Saphenous Vein (SSV) incompetence? (Yes, No)
- Peripheral arterial disease? (Yes, No)

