3.5.1.2 Wound closure at 12 weeks post-treatment

The number and percentage of patients with a wound closure at 12 weeks post-treatment will be presented with a 95% CI. This will be derived as any wounds that closed on or prior to the 12 week visit in the EDC.

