3.5.2.2 VLU recurrence

Of wounds that healed during the registry, the number and percentage of VLU recurrences will be summarized along with 95% CI.

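### The SAP provides for two target wounds in bilateral patients against the one-wound rule, without declaring it, fixing the unit of analysis or allowing for within-patient correlation

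*SAP*

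**What the plan says.** Protocol 5.2 covers patients with several qualifying wounds: "If more than one wound meets eligibility criteria, Investigator determines which wound to evaluate as the primary". It continues: "All endpoint measurements are collected for the primary wound". SAP 1.1 repeats the rule: "Investigator determines which wound to evaluate as the primary/target wound".

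Later SAP sections provide for a second wound:

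- Section 3.3.1 (disposition) includes "Number and percentage of bilateral patients (2 target wounds".
- Section 3.3.2 has the item "Leg of target wound (Right, left, both", and then: "Additionally, the following information will be summarized for each target wound". Section 3.4.1 summarises index treatment by target wound.
- Section 4.3, step 6, refers multiple wound IDs for clinical review only when the patient is not bilateral. Bilateral patients may therefore carry more than one wound ID into the analysis data.

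SAP section 2, which lists departures from the protocol analysis, covers the interim analysis, the wound index, the pain scale and the subgroups. It does not mention second target wounds.

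The endpoint sections use different units. Section 3.5.1.2: "The number and percentage of patients with a wound closure at 12 weeks post-treatment will be presented with a 95% CI"; its next sentence derives this from wounds closed by the 12-week visit. Section 3.5.1.3 censors unclosed wounds. Section 3.5.2.1 counts wounds, as does section 3.5.2.2: "Of wounds that healed during the registry, the number and percentage of VLU recurrences". Section 3.5.2.6 censors the patient. Section 3.6 (Cox models) names no unit.

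**The concern.** There are two separate problems.

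First, the SAP contradicts the protocol and its own section 1.1 without saying so, and gives no rule for a patient with one closed and one open wound. Two programmers could produce different 12-week closure rates from the same data, and the denominators could change from table to table.

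Second, Clopper-Pearson intervals, the log-log Kaplan-Meier intervals and ordinary Cox intervals all assume independent units. Two legs of one patient share age, mobility and compression habits, so their outcomes are likely to be positively correlated. Counting both as independent overstates the information. The registry tests no hypothesis (SAP 1.1.1), so its estimates and intervals are its main product.

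**Working it through.** The plan gives no precision figure to reproduce. It has no sample size calculation, and the figure of about 200 patients is a feasibility number. The documents do not state the bilateral share, the within-patient correlation or the expected closure rate, so all three are assumed below and shown as ranges.

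**1. Unit by endpoint**

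| Endpoint | SAP section | Unit as worded |
|---|---|---|
| 12-week closure | 3.5.1.2 | patient, derived from wounds |
| Time to closure | 3.5.1.3 | wound |
| Closed at 3 months after closure | 3.5.2.1 | wound |
| Recurrence | 3.5.2.2 | wound |
| Ulcer-free weeks | 3.5.2.6 | patient |
| Cox models | 3.6 | not stated |

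The general time-to-event text in section 3.1 counts patients, although section 3.5.1.3 counts wounds.

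**2. Width of wound-level intervals**

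Let b be the share of contributing patients with two wounds in the denominator, and ρ the within-patient correlation. N patients give N(1+b) wounds. Relative to independent wounds, the variance is inflated by

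DE = [(1−b) + b(2+2ρ)] / (1+b) = 1 + 2bρ/(1+b),

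and the naive interval is too narrow by 1 − 1/√DE.

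| b | ρ = 0.3 | ρ = 0.5 | ρ = 0.8 |
|---|---|---|---|
| 5% | DE 1.03, 1.4% | DE 1.05, 2.3% | DE 1.08, 3.6% |
| 10% | DE 1.05, 2.6% | DE 1.09, 4.3% | DE 1.15, 6.6% |
| 20% | DE 1.10, 4.7% | DE 1.17, 7.4% | DE 1.27, 11.1% |

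Example: 200 patients, b = 20% and ρ = 0.5 give 240 wounds and an effective number of 240/1.167 = 206. At 50%, the normal-approximation half-width is 1.96√(0.25/206) = 6.8 points, against 1.96√(0.25/240) = 6.3 points if the wounds are taken as independent.

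The formula is for a proportion. For the Kaplan-Meier and Cox intervals it is only a guide to size.

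**3. Coverage of the naive exact interval**

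Clopper-Pearson is conservative, so nominal narrowing does not translate fully into lost coverage. Coverage of the 95% interval on wounds was simulated for 50, 75 and 200 patients, closure rates of 50% and 70%, and ρ from 0.3 to 0.8 (100,000 replicates per setting). It ranged from 93.3% to 96.4% at b = 10%, and from 92.5% to 96.5% at b = 20%.

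**4. Either-wound or both-wounds rule for 12-week closure**

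With a wound closure probability of 0.5, P(both closed) = 0.25 + 0.25ρ and P(either closed) = 0.75 − 0.25ρ. Relative to one wound per patient, the either-wound rule adds b(0.25 − 0.25ρ), and the both-wounds rule subtracts the same amount.

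At b = 10%:

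- ρ = 0.3: 0.10 × 0.175 = 1.75 points
- ρ = 0.5: 0.10 × 0.125 = 1.25 points
- ρ = 0.8: 0.10 × 0.05 = 0.5 points

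At b = 20% and ρ = 0.5 the shift is 0.20 × 0.125 = 2.5 points, so the two rules give 52.5% and 47.5%.

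**The case against.** Several counter-arguments have weight.

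- **The one-wound note is about cluster wounds.** It opens that way, but its next sentence covers any patient with more than one eligible wound. Bilateral ulcers are not exempt. This does not stand.
- **The primary exact interval is per patient.** This stands. A reader might infer that all the exact and Kaplan-Meier intervals treat every wound as independent. The documents do not support that: 12-week closure and ulcer-free weeks are worded per patient. Clustering does not arise in a correctly formed patient-level proportion; there the fault is the missing combination rule.
- **The derivation sentence in section 3.5.1.2 may only be a timing rule.** It can fairly be read as saying that closure by the 12-week visit counts, without meaning that either wound is enough. This stands, so the upward shift is conditional on one reading.
- **The loss is small and no test depends on it.** This largely stands. At 10% bilateral and ρ = 0.5 the nominal narrowing is about 4%, and some simulated settings kept coverage above 95%.
- **The eCRF and the table mock-ups, which are separate documents, may fix the unit.** They may. That limits any statement about how the tables will be produced, but it does not explain why section 2 omits the change.

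**Conclusion.** The contradiction is certain from the text: one primary wound in Protocol 5.2 and SAP 1.1, two target wounds in SAP 3.3.1, 3.3.2 and 4.3, and no declaration in section 2. The mixed unit is equally clear and affects primary endpoints. These two faults carry the point.

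The effect on precision is real but modest. It is confined to wound-level analyses: time to closure, 3-month durability, recurrence, and the Cox models if they are run on wounds. Those intervals tend to be too narrow, nominally by 1–11% for 5–20% bilateral and ρ of 0.3–0.8, and part of this is offset where Clopper-Pearson is used.

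A reader might infer that an either-wound reading adds 2.5 points to a 50% closure rate at 10% bilateral. That requires the two legs to be independent (0.10 × 0.25), which conflicts with the correlation behind the interval concern. With ρ between 0.3 and 0.8 the gain is 0.5–1.75 points. A reader might also infer that the protocol requires the primary wound to be chosen before first treatment. It leaves the choice to the investigator and sets no time, although section 8.2.5 has the location of the index wound examined at screening.

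**What to change.** Preferred: state in the SAP that every endpoint is analysed on one primary wound per patient, consistent with Protocol 5.2. Identify that wound from baseline data without reference to outcome, and put second-leg wounds in a listing only. The existing exact, Kaplan-Meier and Cox methods then need no clustering adjustment for second wounds.

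If both legs are kept:

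- declare this in SAP section 2 and reconcile it with Protocol 5.2 and SAP 1.1;
- use the wound as the unit throughout, including 12-week closure and ulcer-free weeks;
- use patient-clustered intervals (robust variance or a bootstrap that resamples patients) for closure, durability, recurrence, Kaplan-Meier and Cox;
- report the one-wound-per-patient analysis as sensitivity.

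The first option needs only SAP wording, and a few second wounds leave the main tables. The second adds some programming and makes the wound-level intervals slightly wider.
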